## **7. HUMAN SUBJECTS CONCERNS**

### **Sources of Materials**

The sources of the research material will be data collected in the course of the clinical trial to determine the efficacy and also to ensure the safety of study participants. The principal types of data will be clinical rating scales and standardized tests (e.g., IQ test and the CELF-4). Routine laboratory measures (blood chemistry, blood cell counts) and biomarkers will be obtained.

Full Study Title: Effect of a Wide Spectrum Nutritional Supplement on Mitochondrial Function in Children with Autism Spectrum Disorder (ASD)

Principal Investigator: [name]; Co-Investigators: [name]

Sponsor: [name]; IND 142751; ClinicalTrials.gov ID: NCT03835117; Protocol Version 02/11/2022

Funding Source: Turnabout for Autism (Private Foundation), Pleasanton CA.

## **Future Studies**

Although the long-term use of the SpectrumNeeds and QNeeds multivitamin is believed to be safe, long-term tolerability and therapeutic effect has not been evaluated. Furthermore, the optimal length of treatment is not known. Further studies will identify the optimal treatment for this therapy and long-term safety.

The biomarkers to be collected for future research include DNA, and RNA. These samples will be collected and sent to [name] laboratory for storage for future analysis such as gene expression, epigenetics, gene sequencing, proteomics or metabolomics.

## **Potential Risks**

The risks associated with these procedures include exposure to the study supplement or placebo, and the risk associated with venipuncture. The blood draws poses a possible risk of bruising at the site of the draw, light-headedness and fainting along with a remote chance of infection.

Although highly unlikely, there are potential privacy risks associated with participating in such a study. There is minimal risk associated with the completion of rating scales and assessment measures. Blood draws are common procedures and will be performed by a certified phlebotomist. We will offer a numbing cream prior to the blood drawing procedure. We will systematically review adverse at follow up phone calls and clinic visits (see below). Parents will be given phone numbers of the principal investigator and study physician – who will be available after hours. The PI and study physician have access to the pharmacy after hours – if it is necessary to break the blind.

The nutritional supplement and supplements similar to it have been on the market and used widely in the autism community. There have been few reported side effects of this supplement. They include nausea and hyperactivity, both of which resolve on their own. One similar supplement produced by [name] at Arizona State University has been studied in three clinical trials without reported significant adverse effects. In addition, the majority of the ingredients in the nutritional supplement are well within the proposed upper tolerable limits recommended by the institute of medicine and the two vitamins that exceed these limits are known to be well tolerated at doses well above the recommend upper limits. Increased consumption of B vitamins may also temporarily change urine color.

Confidentiality will be maintained throughout the project period. With the exception of tests that require date of birth, research records will not include names or contact information. Subjects will be identified only by their code numbers. A file with personal health information (e.g., names and addresses) will be kept separately in a locked file cabinet.

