Full Study Title: Effect of a Wide Spectrum Nutritional Supplement on Mitochondrial Function in Children with Autism Spectrum Disorder (ASD)

Principal Investigator: [name]; Co-Investigators: [name]

Sponsor: [name]; IND 142751; ClinicalTrials.gov ID: NCT03835117; Protocol Version 02/11/2022

Funding Source: Turnabout for Autism (Private Foundation), Pleasanton CA.

	Synopsis
Protocol Title	Effect of a Wide Spectrum Nutritional Supplement on Mitochondrial Function in Children with Autism Spectrum Disorder (ASD)
IRB	WCG Institutional Review Board
Protocol Ver	Wednesday, August 3, 2022
Sponsor	[name], Rossignol Medical Center, Phoenix AZ
IND # / FDA	IND 142751; FDA Division of Psychiatry; Protocol Version 1.4
NCT ID	NCT03835117
Principal Investigator	[name], PhD, Rossignol Medical Center, [name]
Site- Investigator	[name], Southwestern Autism Resource and Research Center (SARRC), Phoenix AZ
Co-Investigators	1. [name], Director of CNNH NeuroGenomics Program, Center for Neurological and Neurodevelopment Health, Voorhees, NJ. 2. [name] D.O. (SARRC), Phoenix AZ
Clinical Sites	1. SARRC, Phoenix, AZ
Laboratory Sites	1. Laboratory of [name], State University of New York Downstate—[name] 2. Religen Inc, Plymouth Meeting, PA 3. Laboratory of [name], Icahn School of Medicine at Mount Sinai, NY NY 4. Laboratory of [name] at the University of Oklahoma Health Sciences Center in Oklahoma City, OK 5. 3billion Laboratory in Seoul, South Korea 6. Iliad Inc, Plymouth Meeting, PA
Study Design	Prospective Randomized 24-week Double-Blind Placebo-Controlled Cross-over
Objectives	To evaluate the metabolic effects of a comprehensive wide-spectrum supplement for children with ASD to determine whether it physiologically targets mitochondrial pathways known to be abnormal in children with ASD.
Participants	Up to 50 children, aged 2 years 6 months to 17 years 3 months with confirmed ASD and mitochondrial dysfunction. Participants will have moderate disease severity (clinic global impression of 4 or above) and stable behavioral, education and medical treatment. Those with severe intellectual impairment, disruptive behavior or medical conditions such as epilepsy will be excluded.

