## Investigational Product

Table 2. Daily Serving Size		6.6g	8.8g	11g	13.2 g	Tolerable Upper Intake Levels
Patient Body Weight	Units	15kg-20kg	21kg-40kg	41kg-60kg	61kg-100kg	Age 4-8 years
NeuroNeeds						
Vitamin C (ascorbic acid)	Mg	450	600	750	900	ND
Vitamin D (cholecalciferol)	Mcg	11.25	15	18.75	22.5	75
Vitamin E (d- $\alpha$ -tocopheryl acetate and mixed tocopherols)	Mg	37.5	50	62.5	75	300
Thiamin (as thiamin HCl)	Mg	18.75	25	31.25	37.5	ND
Riboflavin	Mg	18.75	25	31.25	37.5	ND
Niacinamide	Mg	18.75	25	31.25	37.5	15 
Vitamin B 6 (50% as pyridoxine HCl and 50% as pyridoxal-5-phosphate)	Mg	15	20	25	30	40
(6S)-5-methyltetrahydrofolic acid	mcg	1250	1667	2084	2500	ND
Calcium folinate	mcg	1250	1667	2084	2500	400 
Vitamin B 12 (as methylcobalamin)	Mcg	375	500	625	750	ND
Biotin	Mcg	750	1000	1250	1500	ND
Pantothenic acid (as D-Ca pantothenate)	Mg	225	300	375	450	ND
Calcium	Mg	45	60	75	90	2,500
Iodine (as K iodide)	Mcg	75	100	125	150	300
Magnesium (Mg citrate and Mg malate)	Mg	150	200	250	300	110
Zinc (Zn gluconate)	Mg	9	12	15	18	12
Selenium (as selenomethionine)	Mcg	37.5	50	62.5	75	150
Manganese (as manganese amino acid chelate)	Mg	0.75	1	1.25	1.5	3
Chromium (Cr picolinate)	mcg	37.5	50	62.5	75	ND
Molybdenum (Na molybdate)	mcg	75	100	125	150	600
Potassium (K citrate)	mg	37.5	50	62.5	75	
Creatine monohydrate	mg	937.5	1250	1562.5	1875	
L-Arginine	mg	750	1000	1250	1500	
Carnitine Blend (acetyl L-carnitine HCl and L-carnitine)	mg	375	500	625	750	
Alpha ketoglutaric acid	mg	225	300	375	450	
Ubiquinone	mg	187.5	250	312.5	375	
Choline bitartrate	mg	112.5	150	187.5	225	1000
Inositol	mg	75	100	125	150	
Alpha lipoic acid	mg	75	100	125	150	
D-Beta, D-Gamma, D-Delta tocopherols	mg	3.3	4.4	5.5	6.6	300
QNeeds						
Ubiquinol (QNeeds) 	mg	200	300	400	400	

Full Study Title: Effect of a Wide Spectrum Nutritional Supplement on Mitochondrial Function in Children with Autism Spectrum Disorder (ASD)

Principal Investigator: [name]; Co-Investigators: [name]

Sponsor: [name]; IND 142751; ClinicalTrials.gov ID: NCT03835117; Protocol Version 02/11/2022

Funding Source: Turnabout for Autism (Private Foundation), Pleasanton CA.

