The nutritional supplement used will be a combination of SpectrumNeeds and QNeeds, both produced by NeuroNeeds (Old Lyme, CT; See Table 1). Weight based dosing will be used. The daily serving size will be divided into two daily doses in the form of a powder which can be mixed into liquid or food. Together, there are 34 different dietary supplements in the products. Thirty-two of the 34 supplements do not exceed the Tolerable Upper Intake Limits set by the United States Institute of Medicine. The exceptions are:

1. The niacin dosing is about the upper limit. Niacin in the form of nicotinic acid is well known for causing benign flushing. Niacinamide (also known as nicotinamide) is the form of niacin in SpectrumNeeds, and this form does not cause flushing.
2. Folate exceeds the upper limit. It should be noted that half of the total folate provided is in the form of Quatrefolic™ (6S)-5-Methyltetrahydrofolic acid Glucosamine salt (55% FOLATE), which is microbial sourced, not synthetic. There is no known upper tolerable limit for non-synthetic folate, only for synthetic folate. The other half is in the form of calcium folinate. Dosage of folate used in this supplement are about one-half that commonly recommended during pregnancy to women with a prior child with a neural tube defect who may get pregnant. Dosages of folinate are one half to one-twenty-fifth the dosing commonly recommended in children with ASD. These dosages are known to be generally well tolerated in ASD children.

Except for ubiquinol, all of these nutrients are provided in a powder form in SpectrumNeeds. The physical stability and bioavailability of ubiquinol is insufficient in powder form, and thus ubiquinol is provided separately in QNeeds gel capsules. These capsules can be swallowed whole, or cut with scissors and the contents squeezed out and added to SpectrumNeeds just before ingestion.

Placebos will have the same look, feel and taste as the active treatments. For example, the SpectrumNeeds is a silica powder flavored by monk fruit extract, so the inert silica powder with the same flavoring will be used as a control. Similarly, in QNeeds, the ubiquinol is carried by purified water and glycerin colored by caramel liquid, so for the placebo the same carrier and color will be used in the gel capsule without ubiquinol.

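### The upper-limit statements in the dose justification and risk text do not agree with Table 2: niacin is at least 1.25 times its printed limit, three or four rows exceed their limits rather than two, and limits are printed for ages 4-8 only

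*Combined protocol and SAP*

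**What the plan says.** Three places in the combined protocol and SAP compare the supplement with upper intake limits.

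- **Section 5, Investigational Product, text.** "Thirty-two of the 34 supplements do not exceed the Tolerable Upper Intake Limits set by the United States Institute of Medicine". Two exceptions follow. For niacin, "The niacin dosing is about the upper limit", with the comment that the form used does not cause flushing. For folate, "Folate exceeds the upper limit", with an explanation of the two forms supplied.
- **Section 5, Table 2.** Four weight bands (15-20, 21-40, 41-60 and 61-100 kg), with the daily amount of each component in each band and one column of upper limits, headed for ages 4 to 8 years. The niacinamide row reads "Niacinamide Mg 18.75 25 31.25 37.5 15".
- **Section 7, Potential Risks.** "the majority of the ingredients in the nutritional supplement are well within the proposed upper tolerable limits", and "the two vitamins that exceed these limits are known to be well tolerated" at doses well above those limits.

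The Synopsis gives the participants as "Up to 50 children, aged 2 years 6 months to 17 years 3 months". The inclusion criteria set the weight range at 15 to 100 kg, and serving size depends on weight alone.

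**The concern.** The comparison with upper limits is one of the few quantitative safety arguments in the plan, and the risk section relies on it. Table 2 lets a reader check it, and the check fails in three ways. The niacin wording suggests an amount near the limit, where the table shows an amount clearly above it. The count of components that do not exceed is higher than the table allows. The statements carry no age qualifier, although the only printed limits are for one age group in a trial with a much wider age range.

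At stake is whether the ethics board, the medical monitor and parents are given the margin that the plan's own table shows. The efficacy analysis is not affected.

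**Working it through.** **Inputs.** Amounts and limits are from Table 2. The 32-of-34 figure is from the Investigational Product text. Ages are from the Synopsis and the inclusion criteria.

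**1. Count the rows.** Table 2 has 31 component rows: 14 with a numeric limit, 8 marked ND and 9 blank (14 + 8 + 9 = 31).

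**2. Try to reproduce 32 of 34.** Use the reading most favourable to the plan: every ND or blank row counts as not exceeding, and so does any of the 34 supplements without a row of its own. Ratio = daily amount / printed limit. The rows that exceed in at least one band are:

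| Row (limit) | 15-20 kg | 21-40 kg | 41-60 kg | 61-100 kg |
|---|---|---|---|---|
| Niacinamide (15 mg) | 18.75/15 = 1.25 | 25/15 = 1.67 | 31.25/15 = 2.08 | 37.5/15 = 2.50 |
| Calcium folinate (400 mcg) | 1250/400 = 3.13 | 1667/400 = 4.17 | 2084/400 = 5.21 | 2500/400 = 6.25 |
| Magnesium (110 mg) | 150/110 = 1.36 | 200/110 = 1.82 | 250/110 = 2.27 | 300/110 = 2.73 |
| Zinc (12 mg) | 9/12 = 0.75 | 12/12 = 1.00 | 15/12 = 1.25 | 18/12 = 1.50 |
| **Rows above limit** | **3** | **3** | **4** | **4** |
| **Not exceeding, of 34** | 34 - 3 = **31** | **31** | 34 - 4 = **30** | **30** |

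No band gives 32. Magnesium exceeds its printed limit in every band, and zinc does so from 41 kg. Neither is named as an exception.

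**3. Niacin.** The lowest multiple is 1.25, or 25% above the printed limit. That figure does not depend on applying the limit for ages 4-8 to heavier children. The higher multiples increasingly do.

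**4. The majority statement.** Of the 14 rows with a limit, 14 - 4 = 10 are below it in all four bands: 10/14 = 71%. Nine of these ten are at or below half the limit even in the top band; vitamin B6 reaches 30/40 = 75%. Against all rows the share is 10/31 = 32%. If the nine blanks are limits lost when the table was read, and all nine rows met them, the share would be (10 + 9)/31 = 61%. So the share of all rows shown to be within a limit lies between 32% and 61%, depending on how the blanks are read. The eight ND rows cannot be shown to be within any limit on either reading.

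**5. Ages covered.** The enrolled span is 17.25 - 2.5 = 14.75 years. Ages 4 to 8 (up to the ninth birthday) cover 5 years, or 34%. Below that lie 4 - 2.5 = 1.5 years (10%), and above it 17.25 - 9 = 8.25 years (56%). These are shares of calendar years, not of participants, because the plan gives no expected age distribution.

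**The case against.** The strongest reply has four parts.

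- **The majority sentence is defensible.** On its ordinary reading, of the ingredients that have a limit most are well inside it, and 10 of 14 are. This stands. A reader might infer from 10 of 31 that the sentence is false, but that counts 17 rows without a printed limit as failures. For those rows the sentence is unsupported, not disproved.
- **The niacin excess is disclosed.** Niacin is listed as an exception, and the risk text says that two vitamins exceed their limits; *about* may be a slip for *above*. This also stands, so the plan cannot be said to hide the excess. What remains is wording that understates the size and conflicts with the risk section.
- **The upper-band multiples use a limit for ages 4-8.** A reader might infer that the heaviest participants receive 2.5 times their own limit. The documents do not support that, because they print no limit for other ages. The same caution applies to zinc above 41 kg. It does not rescue the count of 32, because niacinamide, folinate and magnesium already exceed in the lowest band.
- **Magnesium and zinc are minerals.** The phrase about two vitamins could therefore be literally true. But the 32-of-34 count covers all supplements, and the risk text mentions no exceedance beyond those two.

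Two features of the table are not errors. Having 31 rows for 34 supplements is compatible with rows that combine ingredients, such as the tocopherols and the carnitine blend. Footnote text may also have been lost in extraction. If any blank cell hid a limit that was exceeded, the count of exceedances would only rise.

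**Conclusion.** The concern holds as a matter of reconciliation and reporting. Three statements need correcting:

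1. Niacin is above its printed limit in every band, by a factor of 1.25 in the lowest and up to 2.5 in the highest if the limit for ages 4-8 is applied there.
2. The 32-of-34 count is not reproduced. On the most favourable reading it is 31 in the two lower bands and 30 in the two upper bands.
3. The comparison is stated without qualification, yet it has a numeric limit for only 14 of 31 rows and no printed comparison for children under 4 or over 8.

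The documents do not support the broader inference that the safety text as a whole misdescribes the doses given. Most components with a printed limit are below it in every band, and two exceedances are acknowledged. The result rests on Table 2 as printed, on treating each row as one component, and on zinc at exactly its limit (21-40 kg) counting as not exceeding. No view is taken on which amount or limit is right.

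**What to change.** Reconcile Table 2, the Investigational Product text and Potential Risks in one amendment:

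- State how many components have a limit, how many exceed it in each weight band, and which they are. Confine the claim of being well within limits to components that have one, and say that the rest have none.
- Replace *about* for niacin with its actual multiple in each band.
- Add the limits for every enrolled age group, including under 4 and over 8. Compare each weight band with the age groups that can fall in it. These limits are not in the documents and must come from the sponsor's source.
- Restate or remove the 32-of-34 figure, and carry the corrected statement into the risk text.

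The cost is table and wording changes, plus a stated safety margin that will look less favourable. No change of dose or limit is proposed here.

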## **Recruitment**

The research team will use targeted recruitment, such as posting to the local website, contacting clinical populations, using social media and contacting local organizations, physicians and schools. All recruitment materials such as flyers, letters and social media posts will be IRB approved. There must be a suspicion of mitochondrial dysfunction for the participants to qualify for the study.

## **Compensation**

Subjects will be compensated \$50 for the following visits: screening, baseline, end of Phase 1 and end of Phase 2.

## **Consent Process**

Full Study Title: Effect of a Wide Spectrum Nutritional Supplement on Mitochondrial Function in Children with Autism Spectrum Disorder (ASD)

Principal Investigator: [name]; Co-Investigators: [name]

Sponsor: [name]; IND 142751; ClinicalTrials.gov ID: NCT03835117; Protocol Version 02/11/2022

Funding Source: Turnabout for Autism (Private Foundation), Pleasanton CA.

Interested families will be screened on the telephone by the study coordinator. Presumably eligible and willing families will be invited to the site for a formal screening visit. Parental consent will be obtained at the screening visit prior to the collection of any study data. The consent procedure will include the following: (a) provide the consent forms to parents and guardians together with a verbal summary of the contents of all paragraphs, and (b) a description of alternatives to participating in the study (not to take part, use of other treatments, and obtaining similar treatment through other clinical services). Parents (guardians) will also be told that declining participation will not prejudice their right to pursue other treatments at the local site or any of its affiliates.

Parental consent will be obtained by trained investigators as documented on each sites delegation of authority log. Children whose parents indicate notable barriers to meeting the demands of the study or whose parents lack capacity to understand the purpose and expectations of the study will not be randomized in the study. These judgments will be made by the investigator conducting the consent discussion in consultation with the research team as needed. Parents will be given the opportunity to ask questions. Once all questions have been answered, parent(s) will be asked to sign and date the consent form. Parents will be provided with a copy of the signed consent form.

Child Assent: The children in this study will be diagnosed with ASD. Most will also be cognitively delayed. The site investigator or designated Co-investigator conducting the consent procedure will evaluate the child's capacity to provide written or verbal assent. The investigator's judgment will be documented on the assent form.

Consent for Video Recording Consent for video recording for research purposes will be obtained from parents. If parents are willing, video recordings will be used for verifying behavioral scoring but additional observers, monitoring of the testing for ensuring high quality evaluations and training evaluators. Parents can indicate agreement or disagreement with this additional use of the videos directly on the video consent form. Agreement to use the videos for these additional training purposes is not required for study participation.

Parental Consent for Saliva Biological parents may choose to provide saliva samples. This is not required for child participation in the study. Parents will be asked to accept or decline by initialing under the "Making Your Choice" option in the future and genetic research sections. There will also be a separate consent page for each biological parent at the end of the consent form. If one of the parents is unable to consent to providing saliva at the time of initial consent, they may return to the clinic and be consented by the PI at a later date. This will be documented in the subject record, and the family will be provided a copy of the updated consent form.

Study Withdrawal Parents are free to withdraw from the study at any time. This will be clearly stated during the consent process. Subjects may need to discontinue participation in the study before completion for various reasons (e.g., family move, withdrawal of consent, adverse events, need for a different treatment). Parents who indicate intention to withdraw the child from the study will be offered to have a case conference with the study team to discuss the matter. If the discussion indicates that the child needs another treatment, we will assist the family to locate that treatment. Parents who drop out of treatment will be invited to return for scheduled assessments or an early termination visit. Data collected from children who drop out of treatment, but return for assessments, will be analyzed in their originally randomized group.

## CONFIDENTIALITY

Full Study Title: Effect of a Wide Spectrum Nutritional Supplement on Mitochondrial Function in Children with Autism Spectrum Disorder (ASD)

Principal Investigator: [name]; Co-Investigators: [name]

Sponsor: [name]; IND 142751; ClinicalTrials.gov ID: NCT03835117; Protocol Version 02/11/2022

Funding Source: Turnabout for Autism (Private Foundation), Pleasanton CA.

Case report forms (CRFs) contain the subject's unique ID number – but no identifying information. The RedCap Clinical Trial Management System is a secure, password protected data base. The folders containing CRFs data will be kept in locked files and access to these files is only granted to members of the research team. Standardized tests (e.g. IQ and language tests) record will not record the child's date of birth but will use age calculate normative data. No other personal health information will be documented on research forms. Contact information for the family is kept in a separate file that is in a locked cabinet.

Certain measures will be recorded on video. The digital files are stored on a secure, password-protected site. Recordings may also be stored electronically on an encrypted external hard drive that is kept in a locked closet or cabinet. The digital files will be marked with a Subject ID instead of names of children or their parents. It is possible that names may be mentioned on the recordings. Video recordings from this research study will be retained for up to 5 years after the study is over. Recordings may be used for other purposes (e.g. presentations at professional meetings) if separate consent is obtained from the parent (or guardian).

Access to study records (case report forms) will be restricted to study staff. Others that may review research records include study monitors, representatives from Food and Drug Administration (FDA). We may submit de-identified study data to the National Database for Autism Research (NDAR).

